6.2. Analysis Methods

6.2.1. Categorical

Unless specified otherwise, the primary analysis method for the binary categorical efficacy and health outcome variables will be a logistic regression model with treatment, concomitant csDMARD use at baseline, and moderate-to-severe plaque psoriasis involvement as factors. The odds ratios and the corresponding 95% CIs will be reported. Fisher's exact test will be used as the secondary analysis method.

For ordinal categorical variables, a logistic regression model using cumulative logits will be used.

Treatment differences (Absolute Risk Reductions [ARR]), Relative Risks (RR), Numbers Needed to Treat (NNT) estimates, and their corresponding 95% CIs (using normal approximation) will also be reported. See [Appendix 1](#) for more details.

The statistical methodology for assessing noninferiority of ixekizumab to adalimumab for ACR50 is described in [Section 6.7](#).

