6.6. Multiple Comparisons/Multiplicity

A multiple testing procedure for the primary and major secondary endpoints will be implemented to control the family-wise type I error rate at a 2-sided α level of 0.05. The primary and major secondary endpoints will be sequentially tested in the following order to compare ixekizumab versus adalimumab, using the primary analysis method.

1. Test 1 for Primary Endpoint – Proportion of patients simultaneously achieving ACR50 and PASI 100 at Week 24: A superiority test of the primary endpoint will be performed at an overall 2-sided $\alpha = 0.05$ using the methods described in Section 6.2.1.
2. Test 2 for Major Secondary Endpoint #1 – Proportion of patients achieving ACR50 at Week 24: If the test for the primary endpoint is significant, then a noninferiority test for the major secondary endpoint #1 will be performed using the methods described in Section 6.7.
3. Test 3 for Major Secondary Endpoint #2 – Proportion of patients achieving PASI 100 at Week 24: If the test for major secondary endpoint #1 is significant, then a superiority test for major secondary endpoint #2 will be performed using the methods described in Section 6.2.1.

If a test in this sequence is not significant, all subsequent tests will be considered nonsignificant.

There will be no adjustment for multiple comparisons for any other analyses.

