6.7. Methodology for Noninferiority Test

For assessing noninferiority of ixekizumab to adalimumab, missing data will be imputed using the NRI method. Noninferiority analysis will be performed on the ITT population using a prespecified fixed margin approach. There is no universally accepted value for what is considered to be a clinically unimportant difference between 2 treatments for a particular efficacy measure. We will consider the points from EMEA Committee for Medicinal Products for Human Use (CHMP) (CHMP 2005) and FDA guidance (2016) which state that an appropriate noninferiority margin should be based on both clinical and statistical grounds.

The null hypothesis will be rejected if the lower bound of the 2-sided 95% CI for the difference in proportions of responders on ixekizumab minus adalimumab is greater than the prespecified margin, meaning ixekizumab will be deemed noninferior to adalimumab. If the lower bound of the CI exceeds 0 (the corresponding p-value from the logistic regression model will also be produced), and ixekizumab will be deemed superior to adalimumab based on the p-value. The 95% CIs for the difference in proportions will be calculated using the simple asymptotic method, without continuity correction (that is, normal approximation to the binomial distribution).

Based on EMEA CHMP (CHMP [WWW]), FDA guidance (FDA [WWW]), and Weinblatt et al. (2013), a noninferiority margin of -12.0% for ACR50 between ixekizumab and adalimumab (ie, response rate of ixekizumab – response rate of adalimumab) is considered appropriate. This noninferiority margin represents an approximately 50% preservation of the adalimumab treatment effect (based on the difference between adalimumab and placebo) observed in a historical Phase 3 study for adalimumab 40 mg twice weekly compared with placebo (Mease et al. 2005) and Study RHAP (Mease et al. 2016).

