6.12. Efficacy Analyses

[Table RHCF.6.3](#) includes the description and derivation of the primary and secondary efficacy outcomes.

[Table RHCF.6.4](#) provides the detailed analyses including analysis type, method and imputation, population, time point, and comparisons for primary and secondary efficacy analyses.

Table RHCF.6.3. Description and Derivation of Primary and Secondary Efficacy Outcomes

Measure	Description	Variable	Derivation/Comment	Imputation Approach if with Missing Components
American College of Rheumatology (ACR) Responder Index	A composite of clinical, laboratory, and functional measures in PsA to assess relief of signs and symptoms; responses are presented as the minimal numeric disease assessment criteria.	ACR20/50/70 Time to first ACR20/50/70 response	See Appendix 2 for details.	See Appendix 2 for details.

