	
 Time to first simultaneous ACR50 and PASI 100 response 	Log-rank Test Kaplan-Meier product limit method	ITT population	IXE vs ADA up to Week 24 and Week 52	Exploratory analysis
		Kaplan-Meier plots (survival curve)	ITT population	IXE vs ADA up to Week 24 and Week 52	Exploratory analysis
American College of Rheumatology (ACR) Responder Index 20, 50, and 70	
 Proportion of patients with ACR20 Proportion of patients with ACR50 (Major Secondary Endpoint at Week 24) Proportion of patients with ACR70 	Logistic regression using the NRI method (see Section 6.4.1)	ITT population	IXE vs ADA at Week 24 and all other post-baseline visits	Major secondary analysis (ACR50: IXE vs ADA at Week 24) Secondary analysis
		Fisher’s exact test using the NRI method (see Section 6.4.1)	ITT population	IXE vs ADA at Week 24 and all other post-baseline visits	Secondary analysis
	
 Time to first ACR20 response 	Log-rank Test Kaplan-Meier product limit method	ITT population	IXE vs ADA up to Week 24 and Week 52	Exploratory analysis

Measure	Variable	Analysis Method (Section 6.2)	Population (Section 6.1.3)	Comparison/Time Point	Analysis Type
	
 Time to first ACR50 response Time to first ACR70 response 	Kaplan-Meier plots (survival curve)	ITT population	IXE vs ADA up to Week 24 and Week 52	Exploratory analysis
Tender Joint Count (TJC) (68 joint count)	
 Change from baseline in TJC Score 	MMRM	ITT population	IXE vs ADA at each post-baseline visit	Secondary analysis
		ANCOVA model using mBOCF (see Section 6.4.2)	ITT population	IXE vs ADA at each post-baseline visit	Secondary analysis
Swollen Joint Count (SJC) (66 joint count)	
 Change from baseline in SJC Score 	MMRM	ITT population	IXE vs ADA at each post-baseline visit	Secondary analysis
		ANCOVA model using mBOCF (see Section 6.4.2)	ITT population	IXE vs ADA at each post-baseline visit	Secondary analysis
Patient’s Assessment of Pain Visual Analog Scale (VAS)	
 Change from baseline in patient’s pain VAS score 	MMRM	ITT population	IXE vs ADA at each post-baseline visit	Secondary analysis
		ANCOVA model using mBOCF (see Section 6.4.2)	ITT population	IXE vs ADA at each post-baseline visit	Secondary analysis

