6.12.1.2. Methodology for Major Secondary Outcomes

The major secondary endpoints are as follows:

1. Proportion of patients achieving ACR50 in each treatment group at Week 24
2. Proportion of patients achieving PASI 100 in each treatment group at Week 24

The analyses of the secondary endpoints will be based on the ITT population in the Open-Label Treatment Period (Period 2) comparing ixekizumab versus adalimumab at Week 24 using methods described in Section [6.7](#) for the major secondary endpoint #1 and using methods from Section [6.2.1](#) for the major secondary endpoint #2. Missing data will be imputed using the NRI method described in Section [6.4.1](#).

A multiple testing procedure, as described in Section [6.6](#), will be used for testing the primary and major secondary endpoints.

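### Does SAP Table RHCF.6.4 make logistic regression, rather than the noninferiority test, the confirmatory analysis of Week 24 ACR50?

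*SAP*

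**What the plan says.** SAP Section 6.12 introduces Table RHCF.6.4 as the table that "provides the detailed analyses including analysis type, method and imputation, population, time point, and comparisons for primary and secondary efficacy analyses". Its row for ACR20, ACR50 and ACR70 response gives the method as "Logistic regression using the NRI method (see Section 6.4.1") and the analysis type for ACR50 as "Major secondary analysis (ACR50: IXE vs ADA at Week 24"). The other response-rate row for the same measures is Fisher's exact test, labelled secondary. No row mentions the −12% margin or Section 6.7.

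The text sections treat ACR50 differently:

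- Section 6.2.1, on categorical methods: "The statistical methodology for assessing noninferiority of ixekizumab to adalimumab for ACR50 is described in" Section 6.7.
- Section 6.6, on the testing sequence: if the primary test is significant, "then a noninferiority test for the major secondary endpoint #1 will be performed using the methods described in Section" 6.7. PASI 100 comes third, and "If a test in this sequence is not significant, all subsequent tests will be considered nonsignificant".
- Section 6.7: noninferiority is concluded when the lower limit of the two-sided 95% interval for the difference in proportions lies above −12%. For a follow-on superiority statement, "the corresponding p-value from the logistic regression model will also be produced".
- Section 6.12.1.2: Section 6.7 applies "for the major secondary endpoint #1 and using methods from Section" 6.2.1 for the second.

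Protocol Sections 10.3.1.3 and 10.3.3.3 give the same order and the same noninferiority rule. Protocol Section 10.1 and SAP Section 5.2 state 78% power for ACR50 noninferiority and, in the same paragraph, 99% (approximately 99% in the SAP) for PASI 100 by Fisher's exact test.

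**The concern.** A table described as giving analysis type and method seems to name the wrong method for one of three confirmatory endpoints. For the primary endpoint and for PASI 100 the labelled row agrees with the text; only ACR50 departs from it. The departure is also one of kind. Logistic regression yields an odds ratio and a superiority p-value, whereas the only margin in the plan is on the difference scale, so noninferiority cannot be judged from the model the table labels.

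ACR50 is the second of three ordered tests. If it fails, PASI 100 cannot be formally claimed however strong its own result. Were the logistic p-value taken as the second test, the PASI 100 claim would almost always be lost at the planning rates.

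A related worry is the 99% power for PASI 100. It takes no account of the preceding test, so a reader might take it as the chance of a formal PASI 100 claim, which cannot exceed the chance of passing ACR50.

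**Working it through.** **Inputs** (SAP Section 5.2, with the interval method from Section 6.7): n = 275 per arm; ACR50 43.8% ixekizumab, 44.1% adalimumab; margin −12%; two-sided 95% interval by the simple normal approximation; PASI 100 46.9% vs 23.7%; composite 31.3% vs 13.6%.

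**1. The plan's own powers.**
SE = √[(0.438×0.562 + 0.441×0.559)/275] = √(0.492675/275) = 0.04233.
Power = Φ[(0.12 + 0.438 − 0.441)/0.04233 − 1.96] = Φ(2.764 − 1.960) = Φ(0.804) = 78.9%.
Summing exact binomial probabilities over every pair of response counts for which the interval lies above −12% gives 79.7%. The stated 78% is reproduced to within 2 points. Exact enumeration of Fisher's test gives 99.99% for PASI 100 and 99.87% for the primary endpoint, in line with the stated 99%.

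**2. What a misreading would cost.** With the same enumeration, a two-sided 0.05 score test (standing in for the stratified logistic model) favours ixekizumab on ACR50 in 2.2% of trials. A superiority result here also satisfies the noninferiority rule, so the two readings of the second step disagree in 79.7 − 2.2 = 77.5, or about 77% of trials.

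**3. Chance of a formal PASI 100 claim.** With the stated 78% for ACR50, the probability that all three tests succeed lies between 0.9987 + 0.78 + 0.9999 − 2 = 77.9% and 78.0%. A simulation of 400,000 trials gives 79.7%. It used the four ACR50-by-PASI 100 cells implied by the planning rates (ixekizumab 0.313, 0.125, 0.156, 0.406; adalimumab 0.136, 0.305, 0.101, 0.458) and pooled z tests in place of logistic regression. Once the first two tests pass, the third passes more than 99.9% of the time, so the ACR50 step sets the figure. With a superiority test as the second step it would be 2.2%.

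**4. Does any part of the plan set the second step that way?**

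| Place | What it fixes for ACR50 at Week 24 |
|---|---|
| SAP 6.2.1 | Noninferiority method: see 6.7 |
| SAP 6.6 | Second test in the sequence: noninferiority by 6.7 |
| SAP 6.7 | Lower 95% limit against −12%; logistic p-value in addition |
| SAP 6.12.1.2 | Endpoint #1 by 6.7 |
| Protocol 10.3.1.3, 10.3.3.3 | Same order and rule |
| SAP Table RHCF.6.4 | Logistic regression row labelled major secondary; no 6.7 row |

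Within the SAP, only Section 6.6 defines the sequence, and it names Section 6.7. The table says nothing about order or about what must succeed before PASI 100. Its method column is headed with a reference to Section 6.2, whose categorical part sends ACR50 noninferiority on to Section 6.7 and also calls for the normal-approximation interval for the treatment difference. The labelled logistic analysis is itself planned, because Section 6.7 asks for its p-value. The row is therefore incomplete rather than a competing instruction.

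**The case for a change.** The best case for an edit is that clear intent elsewhere shows which way to correct the table but does not make the table right. Section 6.12 claims that the table gives type and method, ACR50 is the one confirmatory endpoint where label and text part company, and a plan should name a single method for a test on which another claim depends, particularly in an open-label trial. The edit would cost one added row and one relabelled row. On power, 78% and 99% stand side by side with nothing to say that the second is conditional in practice on the first.

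The factual part of this stands: the row is missing and the label is misplaced. What does not follow is any consequence. The 77% disagreement and the 2.2% claim probability describe a trial whose analysts set aside Sections 6.6, 6.7 and 6.12.1.2 in favour of a table label, and nothing in the plan invites that. The interval needed for the noninferiority decision is produced in any event.

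On power, the 99% is attached to a named single test, is correct for it, and is never offered as the power of the sequence. The 78% ceiling is in the same paragraph and the order of testing is explicit, so annotating the figure is a matter of taste. Doing so in the Synopsis and Section 10.1 would also mean revising the protocol to gloss a correct number.

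**Conclusion.** No change is needed. The mismatch in Table RHCF.6.4 is genuine but clerical: one table row lags behind four SAP sections and two protocol sections that agree with each other. Following the plan as written gives the Section 6.7 noninferiority test as the second step, with power of about 78% to 80% at the planning rates, and a formal PASI 100 claim with much the same probability. Correcting the row would alter no test, order, error rate, sample size or conclusion.

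The power figures rest on the planning rates in the documents and on score, Fisher or pooled z tests standing in for the stratified logistic model; other true rates would move them. The conclusion does not depend on those figures. It rests on the text fixing the ACR50 test without ambiguity.

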5.2. Number of Participants

Approximately 917 participants will be screened (assuming a 40% screen failure rate) to achieve randomization of 550 participants (275 per treatment group) and approximately 396 patients are expected to complete Week 52 (assuming 72% completion rate at Week 52).

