6.4. Handling of Dropouts or Missing Data

6.4.1. Non-Responder Imputation (NRI) for Clinical Response

Analysis of categorical efficacy and health outcome variables will be based on treatment success/failure. This approach yields results numerically identical to non-responder imputation (NRI), but it is interpreted differently. Patients will be considered treatment failures (or non-responders) if they do not meet the clinical response criteria or have missing clinical response data at a particular time point of analysis.

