			score of 0 (not tender) or 1 (tender). Otherwise, if the ratio of the circumference of the digit is ≤ 1.1 , then the LDI-B score is set to 0. Tenderness is assessed in the area between the joints. The results of each digit are then added to produce a total score (Healy and Helliwell 2007).	
		
 Change from baseline in LDI-B 	Calculated as: observed LDI-B score – baseline LDI-B score	Missing if baseline or observed value are missing
		
 LDI-B score = 0 	LDI-B score equals to 0, indicating complete resolution in dactylitis.	Missing if observed value is missing
Disease Activity Score based on C-Reactive Protein (DAS28-CRP)	The DAS28-CRP is a measure of disease activity in 28 joints that consists of a composite numerical score utilizing the following variables: TJC, SJC, hs-CRP (measured in mg/L), and PatGA recorded by patients on a 0- to 100-mm VAS. For DAS28-CRP, the 28 joints to be examined and assessed as tender or not tender for TJC (TJC 28) and as swollen or not swollen for SJC (SJC 28) are a subset of those assessed for the TJC and SJC and include 14 joints on each side of the patient’s body: the 2 shoulders, the 2 elbows, the 2 wrists, the 10 metacarpophalangeal joints, the 2 interphalangeal joints of the thumb,	
 DAS28-CRP score 	The following equation will be used to calculate the DAS28 (Vander Cruyssen et al. 2005): $DAS28 - CRP = 0.56(\sqrt{TJC\ 28}) + 0.28(\sqrt{SJC\ 28}) + 0.36(\ln(CRP + 1)) + 0.014(VAS) + 0.96$ Where TJC 28 is calculated as: (sum of the evaluable individual joint scores)/(number of evaluable joints) × 28; SJC 28 is calculated as: (sum of the evaluable individual joint	If one or more variables are missing, then set to missing.

Measure	Description	Variable	Derivation/Comment	Imputation Approach if with Missing Components
	the 8 proximal interphalangeal joints, and the 2 knees (Smolen et al. 1995).		
scores)/(number of evaluable joints) × 28
 
See Appendix 3 for complete details.
	
		
 • DAS28-CRP <2.6 • DAS28-CRP ≥2.6 and <3.2 • DAS28-CRP ≥3.2 and <5.1 • DAS28-CRP ≥5.1 	
DAS28-CRP score falls in intervals
 
<2.6
 
≥2.6 and <3.2
 
≥3.2 and <5.1
 
≥5.1
	Missing if DAS28-CRP score is missing

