Patient’s Global Assessment of Disease Activity Visual Analog Scale (VAS)	
 Change from baseline in patient’s global assessment VAS score 	MMRM	ITT population	IXE vs ADA at each post-baseline visit	Secondary analysis
		ANCOVA model using mBOCF (see Section 6.4.2)	ITT population	IXE vs ADA at each post-baseline visit	Secondary analysis
Physician’s Global Assessment of Disease Activity Visual Analog Scale	
 Change from baseline in physician’s global 	MMRM	ITT population	IXE vs ADA at each post-baseline visit	Secondary analysis
		ANCOVA model using mBOCF (see Section	ITT population	IXE vs ADA at each post-baseline visit	Secondary analysis

Measure	Variable	Analysis Method (Section 6.2)	Population (Section 6.1.3)	Comparison/Time Point	Analysis Type
(VAS)	assessment VAS score	6.4.2)			
Patient's Assessment of Physical Function Health Assessment Questionnaire– Disability Index (HAQ-DI)	
 Change from baseline in HAQ-DI score 	MMRM	ITT population	IXE vs ADA at each post-baseline visit	Secondary analysis
		ANCOVA model using mBOCF (see Section 6.4.2)	ITT population	IXE vs ADA at each post-baseline visit	Secondary analysis
	
 Proportion of patients with HAQ-DI improvement ≥ 0.35 	Logistic regression using the NRI method (see Section 6.4.1)	ITT population - patients with HAQ-DI ≥ 0.35 at baseline	IXE vs ADA at each post-baseline visit	Secondary analysis
		Fisher's exact test using the NRI method (see Section 6.4.1)	ITT population - patients with HAQ-DI ≥ 0.35 at baseline	IXE vs ADA at each post-baseline visit	Secondary analysis
C-Reactive Protein (CRP)	
 Change from baseline in CRP (mg/L) 	MMRM	ITT population	IXE vs ADA at each post-baseline visit	Secondary analysis
		ANCOVA model using mBOCF (see Section 6.4.2)	ITT population	IXE vs ADA at each post-baseline visit	Secondary analysis
Disease Activity Score based on C-Reactive Protein (DAS28-CRP)	
 Change from baseline in DAS28-CRP 	MMRM	ITT population	IXE vs ADA at each post-baseline visit	Secondary analysis
		ANCOVA model using mBOCF (see Section 6.4.2)	ITT population	IXE vs ADA at each post-baseline visit	Secondary analysis
	Proportion of patients with DAS28-CRP categories:	Logistic regression using the NRI method (see Section 6.4.1)	ITT population	IXE vs ADA at each post-baseline visit	Exploratory analysis

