Measure	Variable	Analysis Method (Section 6.2)	Population (Section 6.1.3)	Comparison/Time Point	Analysis Type
	<2.6 ≥2.6 and <3.2 ≥3.2 and <5.1 ≥5.1	Fisher’s exact test using the NRI method (see Section 6.4.1)	ITT population	IXE vs ADA at each post-baseline visit	Exploratory analysis
Psoriatic Arthritic Response Criteria (PsARC)	Proportion of patients achieving PsARC	Logistic regression using the NRI method (see Section 6.4.1)	ITT population	IXE vs ADA at each post-baseline visit	Secondary analysis
		Fisher’s exact test using the NRI method (see Section 6.4.1)	ITT population	IXE vs ADA at each post-baseline visit	Secondary analysis
Psoriasis Area and Severity Index (PASI)	
 Proportion of patients with PASI 75 Proportion of patients with PASI 90 Proportion of patients with PASI 100 (major secondary endpoint at Week 24) 	Logistic regression using the NRI method (see Section 6.4.1)	ITT population	IXE vs ADA at each post-baseline visit	Major secondary analysis (PASI 100: IXE vs ADA at Week 24) Secondary Analysis (other visits)
		Fisher’s exact test using the NRI method (see Section 6.4.1)	ITT population	IXE vs ADA at each post-baseline visit	Secondary analysis

Measure	Variable	Analysis Method (Section 6.2)	Population (Section 6.1.3)	Comparison/Time Point	Analysis Type
	
 Change from baseline in PASI score 	MMRM	ITT population	IXE vs ADA at each post-baseline visit	Secondary analysis
		ANCOVA model using mBOCF (see Section 6.4.2)	ITT population	IXE vs ADA at each post-baseline visit	Secondary analysis
	
 Proportion of patients with absolute PASI score ≤ 1 or ≤ 2 or ≤ 3 	Logistic regression using the NRI method (see Section 6.4.1)	ITT population	IXE vs ADA at each post-baseline visit	Secondary analysis
		Fisher's exact test using the NRI method (see Section 6.4.1)	ITT population	IXE vs ADA at each post-baseline visit	Secondary analysis
	
 Time to first PASI 75 response Time to first PASI 90 response Time to first PASI 100 response 	Log-rank Test Kaplan-Meier product limit method	ITT population	IXE vs ADA up to Week 24 and Week 52	Exploratory analysis
		Kaplan-Meier plots (survival curve)	ITT population	IXE vs ADA up to Week 24 and Week 52	Exploratory analysis

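### The exploratory DAS28-CRP category analysis applies non-responder imputation to the unfavourable band ≥5.1, so a patient with a missing score counts as not having high disease activity

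*SAP*

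**What the plan says.** SAP Table RHCF.6.4 (Section 6.12) analyses DAS28-CRP in two ways. Change from baseline is a secondary analysis, by MMRM and by ANCOVA with mBOCF. The second entry is "Proportion of patients with DAS28-CRP categories", with the bands "<2.6 ≥2.6 and <3.2 ≥3.2 and <5.1 ≥5.1". It is analysed by logistic regression and by Fisher's exact test, each with NRI, in the ITT population at every post-baseline visit, and is labelled exploratory.

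Three other places decide how a patient without a score is handled:

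- SAP Table RHCF.6.3 sets the band to missing when the score is missing: "Missing if DAS28-CRP score is missing". One missing component makes the score missing.
- SAP Section 6.4.1 gives the imputation: "Patients will be considered treatment failures (or non-responders) if they do not meet the clinical response criteria or have missing clinical response data". It has no reversed coding for an unfavourable category.
- SAP Section 6.2.1 says: "For ordinal categorical variables, a logistic regression model using cumulative logits will be used". The DAS28-CRP row does not name this model, and Section 6.2.1 does not say which level a missing patient takes.

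**The concern.** NRI protects against flattering results because a patient with no data is scored as a failure. That works only when being in the category is a success. The other NRI rows in SAP Tables RHCF.6.4 and RHCF.6.6 are of that kind: ACR and PASI responses, PsARC, MDA, HAQ-DI improvement, resolution scores of zero, mCPDAI ≤5, DLQI (0,1) and treatment satisfaction. DAS28-CRP ≥5.1 is the exception. Applied literally there, the rule removes missing patients from the worst band, so for that band the imputation is anti-conservative.

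Missing scores are likely to be informative. Under Protocol Section 8.1.1, a patient who needs another effective agent for PsA or psoriasis discontinues before starting it. The follow-up schedule in Protocol Section 2 contains no joint counts, patient global assessment or CRP, so later scores cannot be computed. Patients doing badly can therefore leave and then be counted as not ≥5.1.

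**Working it through.** **Inputs from the documents.** Protocol Section 5.2 gives "randomization of 550 participants (275 per treatment group" and "approximately 396 patients are expected to complete Week 52 (assuming 72% completion rate at Week 52". Check: 550 × 0.72 = 396, which matches. Planned non-completion is therefore 28% overall, with no split by arm.

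**Assumptions, for illustration only.** The documents give no rate of DAS28-CRP ≥5.1 and no dropout by arm. Let p be the ≥5.1 rate among observed patients, equal in both arms, from 5% to 30%. Let d be the proportion missing, averaging 28% over the arms and differing by 10 points (23% vs 33%) or 20 points (18% vs 38%). The 28% is only a rough scale for d: SAP Section 6.1 maps early-termination data to the next planned visit, which lowers d, while missing components raise it.

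**Formula.** Literal NRI reports p × (1 − d) for the band. The gap between arms is p × (difference in d). If missingness is unrelated to disease state, the true gap is zero.

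| p | Reported, d = 23% vs 33% | Gap (points) | Reported, d = 18% vs 38% | Gap (points) |
|---|---|---|---|---|
| 5% | 3.85% vs 3.35% | 0.5 | 4.1% vs 3.1% | 1.0 |
| 10% | 7.7% vs 6.7% | 1.0 | 8.2% vs 6.2% | 2.0 |
| 20% | 15.4% vs 13.4% | 2.0 | 16.4% vs 12.4% | 4.0 |
| 30% | 23.1% vs 20.1% | 3.0 | 24.6% vs 18.6% | 6.0 |

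In every line the arm with more dropouts shows less high disease activity. With 275 per arm, none of these gaps reaches p < 0.05 by Fisher's exact test; the smallest p-value is 0.097.

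**If dropouts are sicker.** Assume 10% of observed patients and 50% of dropouts are at ≥5.1, with d = 23% vs 33%.

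- True rates: 0.10 × 0.77 + 0.50 × 0.23 = 19.2%, and 0.10 × 0.67 + 0.50 × 0.33 = 23.2%.
- Reported rates: 0.10 × 0.77 = 7.7%, and 0.10 × 0.67 = 6.7%.

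The arm that is truly 4.0 points worse is reported as 1.0 point better.

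**Sum of the bands.** Each band is reported as its observed share × (1 − d), so the four add to 1 − d. At 28% missing that is 72%, not 100%.

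**Opposite coding.** If missing patients are placed in ≥5.1, the proportion is p × (1 − d) + d. With p = 10% and d = 23% vs 33% this gives 30.7% vs 39.7% (Fisher p = 0.03), although observed rates are equal.

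**The case against.** The strongest reply is that an ordinal model may be intended. The method column of SAP Table RHCF.6.4 refers to Section 6.2, the four bands form one variable entry, and they are ordered. A reader might infer that the SAP breaks its own rule for ordinal variables by testing the bands one at a time. The documents do not establish that: the row is ambiguous, and nowhere says that the bands are tested separately. But the ordinal reading does not remove the problem. The row names NRI and Fisher's exact test, NRI defines only success or failure, and no band is assigned to missing patients.

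A reader might also infer that the reversal affects both upper bands. It does not clearly do so. Being outside ≥3.2 to <5.1 can mean better or worse disease, and the same holds for ≥2.6 to <3.2, so neither middle band has a response direction.

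Nor does the arm with more dropouts look better on DAS28-CRP in general. In the same output its <2.6 proportion is lowered, which is the usual conservative effect.

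Finally, the missingness will be visible. SAP Section 6.1 requires the number of patients with non-missing data in categorical summaries, and Section 6.8 reports discontinuations by arm, visit and reason. That helps an alert reader, but corrects neither the percentages nor the tests.

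**Conclusion.** Wrong as written, of minor severity. Followed literally, the row imputes in the favourable direction for ≥5.1, and for that band only. On the assumed inputs the false gap is 0.5 to 6 points, and the direction can reverse if dropouts are sicker. The size rests on an assumed ≥5.1 rate and assumed dropout differences; the documents do not indicate which arm will lose more patients, and with equal dropout and equal p there is no false gap.

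A reader might infer a threat to the main conclusions. The documents do not support that. The row is exploratory and outside the testing sequence of SAP Section 6.6. The primary and major secondary endpoints are favourable outcomes, for which a missing patient counts as a failure. The DAS28-CRP endpoint listed in SAP Section 4 is change from baseline, which does not use NRI.

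**What to change.** Amend the DAS28-CRP category row of SAP Table RHCF.6.4:

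- Apply NRI, logistic regression and Fisher's exact test only to the favourable cumulative thresholds, DAS28-CRP <2.6 and <3.2.
- Show the four bands descriptively by arm and visit, with a separate row for missing so that the percentages add to 100%. Drop the NRI tests of ≥3.2 to <5.1 and ≥5.1.
- If the cumulative-logit model of Section 6.2.1 is what is meant, name it in the row and state the band given to missing patients. Assigning them to ≥5.1 is conservative but lets dropout drive the result, as the 30.7% vs 39.7% example shows, so the choice needs a stated reason.

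The cost is an edit to one table row. It needs no new data, and under the first two changes there are fewer tests than planned.
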